Participants will be stratified at randomization by country (Non-Japan/Japan). Participants in countries other than Japan will be stratified at randomization according to T2DM status (yes/no). Japanese participants will not be further stratified.

Randomized participants will receive their assigned double-blind study medication for a total of 48 weekly doses. The treatment will be administered by SC injection of 2 pre-filled syringes of study medication in the abdomen according to their assigned treatment arm (see Section 8.4.2). During the Double-Blind Treatment Period (Table 2 in Section 1), participants will be evaluated for safety and efficacy every 4 weeks (\pm 5 days) through Week 24 and every 8 weeks (\pm 5 days) after Week 24 through Week 48.

Participants will then return at Week 52 (\pm 5 days) for a PTFU Visit. Participants who discontinue study medication earlier than Week 48 will have an Early Termination (ET) Visit at the time of study medication discontinuation and will return for a PTFU Visit 4 weeks (\pm 5 days) after the ET Visit.

Participants will return 6 months (\pm 14 days) (1 month is defined as 4 calendar weeks) after the Week 52/PTFU Visit for DXA to assess BMD and for collection of samples for potential immunogenicity testing as well as serum and plasma biomarker samples (see Table 3 in Section 1). Participants at the Week 52/PTFU Visit may need to return at 9 months, 12 months, and 14 months (\pm 14 days) (1 month is defined as 4 calendar weeks) after the Week 52/PTFU Visit if required for immunogenicity testing, as described in Section 8.5.3.6 (see Table 3 in Section 1).

[figure not shown]
Figure 1 Study Design Schematic – Screening to Week 52/PTFU

ET = early termination; PTFU = Post-Treatment Follow-Up; QW = once weekly

^a For participants who discontinue study medication prematurely, liver biopsy will be performed at ET if the participant has completed at least Week 20. If a participant discontinues study participation prior to Week 20 they should consider having a liver biopsy at ET.

Figure 2 Study Schematic – Bone Mineral Density and Immunogenicity Follow-Up Visits After the Week 52/PTFU Visit (visit windows \pm 14 days) (1 month is defined as 4 calendar weeks)

DXA = dual-energy X-ray absorptiometry PTFU = Post-Treatment Follow-Up; QW = once weekly

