Any pregnancy that occurs in a female partner of a male study participant should be reported to sponsor or designee during at least 5 half-lives after product administration (5 days) plus 30 days (duration of ovulatory cycle) for a total of 35 days after the end of the Double-Blind Treatment Period. In order for the sponsor or designee to collect any pregnancy surveillance information from the female partner, the female partner must sign an ICF for disclosure of

this information. Information on this pregnancy will be collected on the Pregnancy Surveillance Form.

Laboratory Test Result Abnormalities

The following laboratory test result abnormalities should be captured on the nonserious AE eCRF page or SAE eCRF page, as appropriate. Paper forms are to be used only in the event that the electronic system is not functioning.

- Any laboratory test result that is clinically significant or meets the definition of an SAE
- Any laboratory test result abnormality that required the participant to have study medication discontinued or interrupted
- Any laboratory test result abnormality that required the participant to receive specific corrective therapy

It is expected that wherever possible, the clinical rather than laboratory term would be used by the reporting investigator (e.g., anemia versus low hemoglobin value).

Potential Drug-Induced Liver Injury

Wherever possible, timely confirmation of initial liver-related laboratory abnormalities should occur prior to the reporting of a potential DILI event. All occurrences of potential DILIs, meeting the defined criteria, must be reported as SAEs (see [Appendix 9](#) for reporting details). **Repeat laboratory testing may be performed locally**, and the results should be promptly communicated to the investigator site.

For the purpose of evaluating a potential DILI, the Baseline value is defined as the mean of the test results from analysis of samples collected during Screening and on Day 1.

Note that the evaluation processes below do not replace SAE reporting per defined criteria in [Appendix 9](#).

Evaluation of Participants with New Elevations of Aminotransferases and/or Total Bilirubin
Repeat laboratory testing (including ALT, AST, fractionated bilirubin and alkaline phosphatase) and physical examination should be performed within 48-72 hours when:

- Participants with normal Baseline aminotransferase (ALT and/or AST) values develop elevations greater than $3\times$ the ULN based upon the central lab, or

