- Procollagen 3 amino terminal peptide
- Tissue inhibitor of metalloproteinases 1 (TIMP-1)

Laboratory Metabolic Markers (to be collected at Screening, Day 1, Week 24, and Week 48/ET).

Participants will fast for 8 hours prior to collection of blood samples for these assessments:

- Low-density lipoprotein cholesterol
- High-density lipoprotein cholesterol
- Triglycerides
- Plasma glucose – *Also used for NAFLD Fibrosis Score*
- Plasma insulin
- Hemoglobin A1c – *also to be collected at Long-Term Immunogenicity Follow-Up Visits as applicable (see Section 8.5.3.6)*

Hepatitis Assessments (to be collected at Screening only- see [Appendix 3](#) for diagnosis and exclusion criteria):

- Hepatitis B core antigen antibody
- Hepatitis B surface antigen antibody
- Hepatitis B surface antigen
- Hepatitis B virus DNA
- Hepatitis C virus antibody
- Hepatitis C virus RNA

Pregnancy Testing (to be collected at each visit through the Week 52/PTFU Visit):

- Serum or urine β -HCG. Women of childbearing potential only. Serum β -HCG to be collected at Screening and serum or urine β -HCG to be collected thereafter according to local laws and regulations and Institutional Review Board/Ethics Committee requirements)
- Follicle-stimulating hormone (Screening only for postmenopausal women)

Hematology (to be collected at each visit through the Week 52/PTFU Visit):

- Complete Blood Count
 - White blood cells, including differential
 - Red blood cells
 - Hemoglobin
 - Hematocrit
 - Platelet count – *Also used for FIB4, APRI, and NAFLD Fibrosis Score*
 - Mean corpuscular hemoglobin (MCH)
 - Mean corpuscular hemoglobin concentration (MCHC)
 - Red cell distribution width (RDW)
- Prothrombin time
- Partial thromboplastin time
- International normalized ratio – *Also used in MELD and Child-Pugh Turcotte scoring*

Blood Chemistry (to be collected at each visit through Week 52/PTFU and at Long-Term

Immunogenicity Follow-Up Visits as applicable [see Section 8.5.3.6]):

- AST – *Used as both safety and efficacy endpoints. Also used for FIB4, APRI, and NAFLD Fibrosis Score*
- ALT – *Used as both safety, efficacy endpoints, and for FIB4, APRI, and NAFLD Fibrosis Score*
- Serum glucose
- Total bilirubin
- Indirect bilirubin
- Alkaline phosphatase
- Lactate dehydrogenase
- Creatinine
- Blood Urea Nitrogen
- Uric acid
- Total Protein
- Albumin – *Also used for NAFLD Fibrosis Score.*
- Sodium
- Potassium
- Chloride
- Carbon dioxide
- Calcium
- Phosphorus
- Glomerular filtration rate

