per group). The increased number of randomized participants occurred following: 1) unexpectedly high enrollment rate in the final month of the enrollment period; 2) several participants who had initially been enrolled into FALCON 1 (MB130-068) were determined (based on central pathology biopsy results) to qualify for FALCON 2 (MB130-069) during the period between the closure of enrollment and completion of randomization; and 3) an unexpected decrease in the actual screen failure rate for subjects entered in the final month of enrollment.

Based on the unmet medical need for patients, the benefit/risk assessment discussed in Protocol [Section 6.3](#), and the strict safety monitoring of all participants, the potential clinical benefit outweighs the risks for those who have chosen to participate in this study. No additional revisions are required to the statistical considerations due to the increased number of randomized participants.

Randomized participants will receive their assigned double-blind study treatment for a total of 48 weekly doses. The treatment will be administered by subcutaneous (SC) injection of 2 prefilled syringes of study treatment in the abdomen according to their assigned treatment arm. During the Double-Blind Treatment Period, participants will be evaluated for safety and efficacy every 4 weeks ( $\pm 5$  days) through Week 24 and every 8 weeks ( $\pm 5$  days) after Week 24 through Week 48.

A schematic of the study design is displayed in [Figure 1](#) (Screening to Week 52/Post-Treatment Follow-up [PTFU]) and [Figure 2](#) (follow-up visits after the Week 52/PTFU Visit).

Sponsor: Bristol-Myers Squibb

Protocol No.: MB130-069

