#### 4.3.5 Clinical Laboratory Parameters

- Absolute and change from baseline values
- Potential hepatotoxicity by time point
  - Aspartate aminotransferase (AST) or alanine aminotransferase (ALT) > 3 x upper limit of normal (ULN) or > 5 x ULN
  - Total Bilirubin > 2 x ULN
  - (AST or ALT) > 3 x ULN and Total Bilirubin > 2 x ULN
- Postbaseline abnormalities defined by the below categories:
  - Serum albumin < 2.8 g/dL
  - Platelet count < 75 x 10^3/ μL
  - Fasting plasma glucose < 60 mg/dL or > 350 mg/dL
  - Fasting triglycerides > 500 mg/dL
  - Estimated glomerular filtration rate (eGFR) < 30 mL/min/1.73 m^2

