### **6.2.4 Clinical Laboratory Parameters**

Based on the safety population, continuous laboratory results will be summarized by visit, treatment group, and pooled BMS-986036 (in both SI units and US Conventional units). Categorical results such as those for urinalysis will be summarized by number and percentage of participants in each category. These summaries will be based on central laboratory results, except in rare circumstances in which only a local lab value is available then a local lab value may be used. This value will be presented in the same unit and summarized with the central results from other participants. Summaries will present both actual and change-from-baseline results for continuous values.

Sponsor: Bristol-Myers Squibb

Protocol No.: MB130-069

Altered postbaseline values will be descriptively summarized by counts and percentages of participants ever experiencing specified altered values at any postbaseline time point.

Laboratory values below the lower limit or above the upper limit of quantification will be imputed to the lower or upper limit, respectively, for summary tables. The actual values will be displayed in the listings.

Box plots will be presented by time point. All laboratory data specified in the summary tables will be present in listings.

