Unscheduled assessments	Unscheduled measurements will be included in the listings. With the exception of unscheduled measurements used for baseline and as specified in section 8.12 , unscheduled measurements will be excluded from the descriptive statistics and statistical analysis.
Prior, Concomitant, and Follow-up Medications	Prior medications are defined as medications taken prior to the first dose of study treatment and discontinued prior to the first dose of study treatment. Concomitant medications are defined as any medication started before/on/after the first dose of study medication until the Week 52/PTFU Visit. Follow-up medications are defined as any medication taken after Week 52/PTFU Visit until the 6 Month Post PTFU Visit that could potentially impact bone mineral density assessments. Any Concomitant medications continued Post Week 52/PTFU will also be considered as Follow-up medication.

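### The combined ALT/AST-and-bilirubin row reads as a same-visit rule, and with off-schedule samples excluded it can omit participants who cross both limits at different times

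*SAP*

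**What the plan says.** SAP 4.3.5 has a bullet headed "Potential hepatotoxicity by time point". Under it are single-analyte rows for aminotransferases and bilirubin, and a combined row, "AST or ALT) > 3 x ULN and Total Bilirubin > 2 x ULN" (opening bracket omitted). No pairing window or maximum-value rule is attached to it. A separate bullet in the same section covers other post-baseline abnormalities.

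SAP 6.2.4 says altered values will be summarised by counts of "participants ever experiencing specified altered values at any postbaseline time point". It does not say how a criterion with two analytes is to be paired.

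On timing, SAP 2.1 states that "participants will be evaluated for safety and efficacy every 4 weeks" to Week 24. Protocol 8.1 gives the same schedule, "through Week 24 and every 8 weeks" from there to Week 48, with a further visit at Week 52. Protocol Table 8 matches this: "Blood Chemistry (to be collected at each visit through Week 52/PTFU".

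Protocol 8.5.3.1 adds off-schedule testing: "Repeat laboratory testing (including ALT, AST, fractionated bilirubin and alkaline phosphatase) and physical examination should be performed within 48-72 hours when" either of two aminotransferase triggers is met. It allows these repeats to be done locally. SAP 8.1 then provides that, apart from baseline and one Fibroscan-related exception, "unscheduled measurements will be excluded from the descriptive statistics and statistical analysis". SAP 6.2.4 uses a local value only in rare cases where no central one exists.

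**The concern.** Bilirubin may rise later than the aminotransferases. If each visit is judged alone, a participant with ALT above its limit at one visit and bilirubin above its limit at the next meets the combined criterion at neither. The single-analyte rows count both elevations but do not show that they belong to the same person.

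The samples most likely to catch both elevations together are the repeats prompted by the first abnormal result. Those are the samples that SAP 8.1 leaves out of the table. Among the summaries described in the SAP, this row is the only one that combines the two analytes, so a zero in it could be misread as no participant having crossed both limits.

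The text also leaves room for two programmers to build the row differently, because neither 4.3.5 nor 6.2.4 states the pairing rule.

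**Working it through.** The plan gives no figure for this row, so there is nothing to reproduce. The check has four steps.

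**1. Visit gaps (Protocol 8.1).** Post-baseline visits fall at Weeks 4, 8, 12, 16, 20, 24, 32, 40, 48 and 52. From Day 1 the gaps are 4, 4, 4, 4, 4, 4, 8, 8, 8 and 4 weeks. With ±5-day windows:
- a 4-week gap can reach 28 + 10 = 38 days;
- an 8-week gap runs from 56 − 10 = 46 to 56 + 10 = 66 days.

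**2. When a case is missed.** On the same-visit reading, the row omits a participant only if no scheduled sample shows both limits exceeded. ALT that is falling but still above 3 x ULN when bilirubin is above 2 x ULN is counted. For an assumed exponential fall from a peak of P x ULN with half-life h days, the time to reach 3 x ULN is h × log2(P/3):

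| Peak (x ULN) | h = 2 days | h = 7 days | h = 14 days |
|---|---|---|---|
| 5 | 1.5 | 5.2 | 10.3 |
| 10 | 3.5 | 12.2 | 24.3 |
| 20 | 5.5 | 19.2 | 38.3 |

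Every entry is shorter than a 56-day gap, and all but the last are shorter than 28 days. ALT could therefore drop below its limit between two scheduled visits.

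**3. Chance that a visit falls in the overlap.** If both limits are exceeded together for w weeks, with w no longer than the gap, the probability is w / gap. For an assumed w = 2 this is 2/4 = 50% up to Week 24 and again from Week 48 to Week 52, and 2/8 = 25% between Weeks 24 and 48. For w = 0 it is 0.

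**4. Same-visit rule against an any-post-baseline rule.** This was simulated on scheduled samples only, for one case with onset uniform over Weeks 0 to 48. D is days ALT stays above 3 x ULN, L the lag to bilirubin above 2 x ULN, and B the days bilirubin stays raised. All three are assumptions.

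| D / L / B (days) | Same visit | Any post-baseline visits |
|---|---|---|
| 28 / 7 / 28 | 56% | 68% |
| 28 / 14 / 28 | 37% | 63% |
| 28 / 21 / 28 | 19% | 56% |
| 42 / 21 / 42 | 56% | 75% |
| 56 / 28 / 56 | 75% | 100% |
| 28 / 28 / 28 (no overlap) | 0% | 50% |

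The second line can be checked by hand. The overlap is 28 − 14 = 14 days, nine visits (Weeks 4 to 48) can catch it, and onset spans 48 × 7 = 336 days, so 9 × 14 / 336 = 37.5%. Even the any-post-baseline rule misses cases when limited to scheduled samples, which is why the unscheduled samples matter.

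**The case against.** The strongest reply is that the same-visit rule is an inference. SAP 4.3.5 never says that both values must come from one sample, SAP 6.2.4 counts participants over any post-baseline time point, and the table shells sit outside the SAP. That stands as a limit on wording: same-visit is the natural reading, not an explicit rule. It does not remove the gap, because no other pairing rule is written down.

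The second reply is that such cases surface elsewhere, and this largely stands. Each elevation is counted in its own row, the laboratory data are listed, potential DILI is reportable as an SAE (Protocol 8.5.3.1 and Appendix 9), and a DMC reviews safety. A reader might infer that this row is the SAP's main screen for serious liver injury; the documents do not support that. The SAE route is only a partial substitute, however. Its definition excludes cases with another apparent cause, including pre-existing liver disease, and every participant here has cirrhosis.

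Third, a reader might argue that the protocol's potential-DILI definition endorses pairing elevations from different dates. It does not. It is silent on timing, and the interruption and discontinuation criteria in Protocol 8.5.3.1 speak of concomitant rises. The case for a participant-level row rests on the sampling schedule, not on that definition.

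Fourth, the durations are hypothetical. That is correct, and the percentages are illustrations only.

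**Conclusion.** The point holds as a low-severity improvement to a safety table. On the natural reading of SAP 4.3.5, a participant whose ALT and AST are at or below 3 x ULN at every scheduled visit where bilirubin exceeds 2 x ULN is absent from the combined row. Gaps of 4 to 8 weeks make this possible, and SAP 8.1 excludes the samples that would narrow them.

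A reader might go further and infer that a case is lost once ALT has begun to fall before bilirubin rises. That is too strong: the case is lost only if ALT and AST have come down to the limit or below by each relevant visit. Nor is it lost to the report, since the omission concerns one row.

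The size depends on assumed durations. In the illustrations above the same-visit rule captures 0% to 75% of such cases and the any-post-baseline rule 50% to 100%. The conclusion assumes that the 48-72 hour repeats are recorded as unscheduled measurements and that the unseen table shells add no pairing rule.

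**What to change.** - Keep the by-visit row in SAP 4.3.5.
- Add a participant-level row counting maximum post-baseline ALT or AST above 3 x ULN together with maximum post-baseline total bilirubin above 2 x ULN, in any order. If a window is preferred, state it and make it long enough to span the 8-week visit gap, which can reach 66 days. A 30-day window could not pair consecutive scheduled visits between Weeks 24 and 48, which are at least 46 days apart.
- Write an exception into SAP 8.1 and 6.2.4 so that unscheduled and local repeat samples count for this table, and state the pairing rule identically in 4.3.5 and 6.2.4.
- Flag participants already above 3 x ULN at baseline, because the entry criteria (Protocol 8.3.2) allow ALT and AST up to 5 x ULN.
- Optionally, plot peak ALT against peak bilirubin by arm.

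The cost is one table row, one flag and a few sentences, with no new data collection. SAP 8.1 already describes the maximum post-baseline value as the highest observed, so little new derivation is needed. The downside is that some unrelated elevations will be paired; the dated listing lets a reviewer separate them.

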#### 4.3.6 Bone Mineral Density Testing (BMD)

BMD as measured by DXA scans of the hip (including femoral neck) and spine that will be performed during the Screening Period and at the Week 48 Visit (or ET, if applicable) as indicated in the Schedule of Activities (protocol [Section 1](#)). Participants will return for a follow-up DXA assessment 6 months (1 month is defined as 4 calendar weeks) after the Week 52/PTFU Visit. DXA may be performed within a window of ± 7 days of the scheduled Week 48/ET Visit and within a window of ± 14 days of the scheduled 6-month follow-up visit. DXA scans will be evaluated by central reading. Following will be summarized.

- Absolute and change from baseline values

#### 4.3.7 Immunogenicity

Immunogenicity (collected at Day 1 and each subsequent visit through the Week 52/PTFU visit and at long-term Immunogenicity Follow-Up visits.

- Proportion of participants with anti-BMS-986036 antibodies (including neutralizing) through Week 52/PTFU and in long-term follow-up

Sponsor: Bristol-Myers Squibb

Protocol No.: MB130-069

- Proportion of participants with anti-FGF21 antibodies (including neutralizing) through Week 52/PTFU and in long-term follow-up

#### 4.4 Pharmacokinetic Endpoints

- Trough (predose) BMS-986036 concentrations from samples collected at each visit

#### 4.5 Exploratory Endpoints

Exploratory endpoints include the following:

- Quantitative measurements of fibrosis and fat on biopsy
  - Assessment of NASH CRN Fibrosis Score at Week 48
    - Proportion of participants with  $\geq 1$  stage improvement
    - Proportion of participants with  $\geq 2$  stage improvement
    - Proportion of participants with  $\geq 2$  stage improvement without worsening of NASH
    - Changes in Fibrosis (as expressed by Shift from baseline)
    - Proportion of participants with  $\geq 1$  stage improvement, no change, or worsening
  - Assessment of Ishak Fibrosis Score at Week 48
    - Proportion of participants with  $\geq 2$  stage improvement
    - Changes in Fibrosis (as expressed by Shift from baseline)
    - Proportion of participants with  $\geq 1$  stage improvement, no change, or worsening
  - Assessment of qFibrosis using digital pathology at Week 48
    - Absolute, percent change, and change from baseline
  - Assessment of CPA at Week 48
    - Proportion of participants with any improvement
    - Absolute, percent change, and change from baseline
  - Assessment of fat and alpha-SMA in stained tissue by morphometry at Week 48
    - Absolute, percent change, and change from baseline
- Assessment of NAS score at Week 48
  - Changes in NAS (as expressed by shift from baseline, for each individual NAS components (Steatosis, inflammation, Ballooning) as well as Total score)
  - Proportion of participants with improvement, no change, or worsening in NAS Total
- Hepatic fat fraction as measured using MRI-PDFF at Week 24 and Week 48
  - Absolute, percent change, and change from baseline
  - Proportion of subjects in each treatment group with  $\geq 30\%$  relative reduction,  $\geq 20\%$  relative reduction,  $\geq 10\%$  relative reduction, and  $\geq 5\%$  absolute reduction
- Noninvasive measures of fibrosis and/or cirrhosis
  - Liver stiffness as determined by Magnetic Resonance Elastography (MRE) at Week 24 and Week 48
    - Absolute, percent change, and change from baseline
    - Proportion of subjects in each treatment group with  $\geq 19\%$  or  $\geq 15\%$  reduction
  - Fibroscan elastography results at Week 48
    - Absolute, percent change, and change from baseline
    - Proportion of subjects in each treatment group with any decrease by time point
- Noninvasive scores of hepatic fibrosis (AST-Platelet Ratio Index (APRI), Fibrosis 4 (FIB-4), Enhanced Liver Fibrosis (ELF), and NAFLD Fibrosis Score) at Week 24 and Week 48
  - Absolute, percent change, and change from baseline
  - Proportion of participants in each ELF category by time point

Sponsor: Bristol-Myers Squibb

Protocol No.: MB130-069

- Metabolic assessments at Week 24 and Week 48
  - Physical assessments (body weight, waist circumference, and body mass index (BMI)) by time point
  - Serum lipids (low-density lipoprotein (LDL), high-density lipoprotein (HDL), and triglycerides (TGs))
    - Absolute and change from baseline
    - Abnormal postbaseline TG values according to thresholds identified in SAP [Section 4.3.5](#)
  - Plasma glucose, Plasma insulin, Hemoglobin A1c
    - Absolute and change from baseline
    - Abnormal postbaseline glucose values according to thresholds identified in SAP [Section 4.3.5](#)
- Child-Pugh Turcotte Score at Week 24 and Week 48
  - Proportion of participants in each Child-Pugh Turcotte class (A, B, C) by time point
  - Shift from baseline according to class (A, B, C)
- MELD Score at each visit through Week 52/PTFU
  - Absolute and change from baseline
- The event rate for any one (first occurrence) of the liver-related clinical outcome events by Week 48
  - Proportion of participants experiencing any of the events by Week 48
  - Proportion of participants experiencing each liver-related clinical outcome event by Week 48
- Patient-reported outcomes at Week 24 and Week 48
  - 3-Level EuroQol 5 Dimension (EQ-5D-3L) Questionnaire
    - Absolute and change from baseline in visual analog score and utility index
    - Proportion of participants in each 3-level dimension by time point
  - 36-Question Short Form Quality-of-Life (SF-36) Questionnaire
    - Absolute and change from baseline in continuous variables described in SAP [Section 8.0](#)
  - Chronic Liver Disease Questionnaire-Nonalcoholic Fatty Liver Disease (CDLQ-NAFLD)
    - Absolute and change from baseline in continuous variables described in SAP [Section 8.0](#)
- Exploratory biomarkers
  - Transaminases
    - ALT normalization (ALT  $\leq$  ULN) at Week 24 and Week 48
    - AST normalization (AST  $\leq$  ULN) at Week 24 and Week 48
    - ALT at each visit through Week 52/PTFU
    - AST at each visit through Week 52/PTFU
    - Change from Baseline (Day 1 predose) ALT levels at each visit through Week 52/PTFU Visit
    - Change from Baseline (Day 1 predose) AST levels at each visit through Week 52/PTFU Visit
  - PRO-C3 (N-terminal type 3 collagen propeptide)
    - Assessment of PRO-C3 levels at each visit through Week 52/PTFU
    - Change from Baseline (Day 1 predose) in PRO-C3 levels at each visit through Week 52/PTFU Visit

Sponsor: Bristol-Myers Squibb

Protocol No.: MB130-069

- Assessment of adiponectin at each visit through Week 52/PTFU
  - Absolute, percent change, and change from baseline

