## 8.0 Conventions and General Definitions

### 8.1 General Definitions

Term	Definition
Study Day	Study day is calculated as: assessment date – date of first dose + 1
Baseline	Unless otherwise stated, Baseline is defined as the last measurement prior to dosing on Day 1 (Week 0). If the measurement on Day 1 is missing or not available, then a prior measurement during the screening period may be used as baseline.
Change from Baseline	Change from baseline is defined as (value at post-baseline visit – value at baseline).
Change in the maximum post-baseline value	Change from baseline in the maximum post-baseline value is defined as highest observed value post-baseline. The change is calculated using this value as the post-baseline value.
Percent Change from Baseline	Percent change from baseline is defined as $([\text{value at post-baseline visit} - \text{value at baseline}]/\text{value at baseline}) \times 100$ . If the baseline value is 0 and the post-baseline value is also 0, then the percent change from baseline is set to 0. Percent change from baseline is not calculated if the baseline value is zero or baseline or post-baseline value is missing.
Study Treatment	For the purposes of the calculations included in this SAP, study treatment will include only doses of BMS-986036 (dose levels of 10 mg QW, 20 mg QW or 40 mg QW) or placebo QW.
Duration of Study Treatment (weeks)	Duration of study treatment in weeks will be defined as: (date of last dose of study treatment – date of first dose of study treatment + 7) / 7.
Treatment Completion (%)	Treatment completion (%) will be calculated as the total number of weeks of treatment received divided by the total number of expected doses (48), multiplied by 100.
End of Study (EOS) Date	The EOS date is the date recorded on the eCRF that a participant either discontinued or completed the study. If the participant is lost

Sponsor: Bristol-Myers Squibb

Protocol No.: MB130-069

	to follow-up, the EOS date will be the date of the last visit assessment obtained.
First Dose Date – Study	The date a participant received their first dose as recorded in the eCRF as date study treatment was administered.
Last Dose Date – Study	The date of last recorded dose on the eCRF for a subject.

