### 8.13 Other Calculations

- ELF assessment combines hyaluronic acid, procollagen 3 amino terminal peptide, and TIMP-1 (tissue inhibitor of metalloproteinases 1). A proprietary algorithm is used to evaluate each of these markers by immunoassay, to create an ELF Score which is provided by an external vendor.
- FIB4 Score =  $(\text{age [years]} \times \text{AST level [U/L]}) / (\text{platelet count } [\times 10^9/\text{L}] \times \text{square root of ALT [U/L]})$ .
- APRI Score =  $([\text{AST divided by AST Upper Limit of Normal}] / \text{platelet count } [\times 10^9/\text{L}]) \times 100$
- NAFLD Fibrosis Score =  $-1.675 + (0.037 \times \text{age [years]}) + (0.094 \times \text{BMI } [(\text{kg/m}^2)]) + (1.13 \times \text{Impaired Fasting Glucose or diabetes [yes = 1, no = 0]}) + (0.99 \times \text{AST/ALT ratio}) - (0.013 \times \text{platelet count } [\times 10^9/\text{L}]) - (0.66 \times \text{albumin } [\text{g/dL}])$ . Note, the status of impaired fasting glucose or diabetes (yes or no) will be assessed only once at baseline as recorded by the site in the Specific Disease History eCRF page. This value will be used for all subsequent calculations.
- MELD Score =  $(9.57 * \ln[\text{creatinine}]) + (3.78 * \ln[\text{Bilirubin}]) + (11.20 * \ln[\text{INR}]) + 6.43$

Note for FIB4, APRI, NAFLD Fibrosis, and MELD scores that if any one component is missing at a given time point, another non-missing value within an absolute range of 3 days may be used. If there is more than one value that is within 3 days, the closest value after the visit date will be selected. Otherwise, if all components are not available the score will not be calculated at that time point.

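### Percent change from baseline is planned for the NAFLD Fibrosis Score, an index that crosses zero, so that one descriptive summary can reverse sign or explode

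*SAP*

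**What the plan says.** SAP 4.5, under noninvasive scores of hepatic fibrosis, names APRI, FIB-4, "Enhanced Liver Fibrosis (ELF), and NAFLD Fibrosis Score) at Week 24 and Week 48". The summary attached to the whole group is "Absolute, percent change, and change from baseline". No exception is made for the NAFLD Fibrosis Score.

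SAP 8.1 defines percent change as the post-baseline value minus the baseline value, divided by the baseline value, times 100. The denominator is the signed baseline, not its absolute value. Two sentences deal with awkward denominators: "If the baseline value is 0 and the post-baseline value is also 0, then the percent change from baseline is set to 0", and "Percent change from baseline is not calculated if the baseline value is zero or baseline or post-baseline value is missing". Negative and near-zero baselines are not mentioned.

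SAP 8.13 gives the NAFLD Fibrosis Score as a linear combination. It has an intercept of -1.675 and positive terms for age, BMI, AST/ALT ratio and an indicator for "Impaired Fasting Glucose or diabetes [yes = 1, no = 0". Terms for platelets and albumin are subtracted.

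Three other places matter:
- SAP 6.4 models change from baseline by ANCOVA for APRI, FIB-4 and NAFLD scores, and its repeated measures model also uses change from baseline.
- SAP 6.5 summarizes continuous data by mean and SD as well as median and quartiles.
- For MELD, SAP 4.5 plans only absolute value and change from baseline.

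**The concern.** A percent change is meaningful on a scale with a true zero and values of one sign. The NAFLD Fibrosis Score has neither, since its zero is simply where the positive and negative terms balance. Two faults follow from the SAP 8.1 definition. If the baseline is negative, a fall in the score (less predicted fibrosis) is reported as a positive percent change and a rise as a negative one. If the baseline is close to zero, a trivial change becomes hundreds of percent. An arm mean then averages numbers whose signs do not share a meaning, and a few participants can dominate it. A reader of the tables could take the direction or the size of the effect wrongly.

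The same SAP definition also gives two incompatible instructions for a baseline of exactly zero. This matters for any variable summarized by percent change that can equal zero.

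**Working it through.** **Inputs.** The score formula is from SAP 8.13 and the percent-change formula from SAP 8.1. Eligibility limits are from protocol 8.3.1 and 8.3.2: age 18 to 75, platelets not below 100 × 10³/µL, albumin not below 3.5 g/dL. Arm size is about 38 (protocol 6.2). The plan states no figure of its own to reproduce here.

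**Step 1: does the score take both signs in eligible participants?**

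NFS = -1.675 + 0.037 × age + 0.094 × BMI + 1.13 × (impaired fasting glucose or diabetes) + 0.99 × AST/ALT - 0.013 × platelets - 0.66 × albumin

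The eligibility limits make the subtracted terms at least 0.013 × 100 = 1.30 and 0.66 × 3.5 = 2.31. Profiles within the age, platelet and albumin limits:

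| Age | BMI | Diabetes | AST/ALT | Platelets | Albumin | NFS |
|---|---|---|---|---|---|---|
| 60 | 36 | yes | 1.1 | 160 | 4.1 | +1.362 |
| 58 | 32 | yes | 0.9 | 230 | 4.4 | -0.394 |
| 55 | 32 | no | 1.0 | 180 | 4.2 | -0.754 |

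The third row is -1.675 + 2.035 + 3.008 + 0 + 0.990 - 2.340 - 2.772 = -0.754. So both signs occur, and a negative value does not require the absence of diabetes.

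**Step 2: sign.** Let the third participant improve to BMI 31, platelets 190 and albumin 4.3. The score becomes -1.675 + 2.035 + 2.914 + 0 + 0.990 - 2.470 - 2.838 = -1.044. Percent change by SAP 8.1 is (-1.044 + 0.754) / (-0.754) × 100 = +38%. The absolute change is -0.290, which has the right sign.

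**Step 3: size.** The same 0.3-point fall, -0.3 / baseline × 100, at different baselines:

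| Baseline | -1.0 | -0.5 | -0.1 | -0.02 | +0.02 | +0.1 | +1.0 | +2.0 |
|---|---|---|---|---|---|---|---|---|
| Percent change | +30 | +60 | +300 | +1500 | -1500 | -300 | -30 | -15 |

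**Step 4: how many participants, and what happens to an arm summary?** The documents give no baseline distribution, so this step is an illustration under assumptions: age 59 (SD 8), BMI 34 (SD 6), AST/ALT median 1.0 (log SD 0.3), albumin 4.2 (SD 0.3), platelet SD 45, and the platelet and albumin limits applied. The true change has mean -0.2 (SD 0.4), an improvement. Arms have 38 participants, with 5,000 arms per row.

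| Platelet mean; diabetes | Baseline < 0 | Baseline within 0.1 of zero | Arm mean, 5th to 95th percentile | Arms with positive mean | Arm median, 5th to 95th percentile |
|---|---|---|---|---|---|
| 140; 75% | 21% | 5.5% | -208% to +186% | 39% | -25% to +2% |
| 165; 70% | 30% | 6.4% | -275% to +233% | 43% | -24% to +7% |
| 190; 60% | 45% | 7.2% | -258% to +279% | 49% | -20% to +16% |

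Two to three participants per arm of 38 lie within 0.1 of zero, and these drive the mean. Modest changes to the assumptions move the low end of the negative-baseline share to about 19%; varying AST/ALT as well takes it to about 14%. With a smaller true change (mean -0.1, SD 0.5) the pattern is the same.

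**Step 5: the zero rule.** Set side by side, the two SAP 8.1 sentences disagree when baseline and post-baseline are both zero: the first assigns 0%, the second says no value is calculated. If the first is read as an exception to the second, 0-to-0 stays in as 0% and 0-to-positive drops out, which is asymmetric.

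**The case against.** The strongest reply is that little depends on this summary. The score is one exploratory endpoint among many. Absolute value and change from baseline are planned beside percent change, both planned models work on change from baseline, and no responder definition or test uses percent change in this score. That stands, and it limits the weight of the point.

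It is also fair that sign reversal affects only participants with a negative baseline; those with a clearly positive baseline get the right sign. The median and quartiles in SAP 6.5 do not explode as the mean does. That stands too, but a median taken over percentages of mixed meaning is still not a measure of direction.

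Three stronger readings are tempting, and the documents do not support them:
- **Improvements in this score are generally reported with the wrong sign.** This holds only below zero, and the share below zero is an assumption.
- **The zero rule biases percent change in morphometric fat or alpha-SMA toward no worsening.** This rests on one of two readings of SAP 8.1, and on zero baselines that the documents do not show. Absolute change is planned for both variables in any case.
- **Percent change is unsuitable, or suitable, for ELF.** The ELF algorithm is proprietary and not given, so nothing can be said either way. APRI and FIB-4 are positive by their formulas and do not share the problem.

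**Conclusion.** The point holds in limited form. That the score crosses zero, that a negative baseline reverses the sign, and that values explode near zero are all arithmetic from the SAP's own formulas and need no assumption. How often this happens does need assumptions: with platelet mean 140 to 190 and diabetes 60% to 75%, roughly 19% to 45% of participants have a negative baseline. An arm's mean percent change is then too unstable to read and is positive in about 39% to 49% of simulated arms despite a true mean improvement.

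The consequence is an unusable descriptive summary for one exploratory score. No primary or secondary result and no planned model is affected. The zero-baseline wording is a real contradiction, but its practical effect cannot be sized from the documents.

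**What to change.** In SAP 4.5, separate the NAFLD Fibrosis Score from the group and plan only absolute value and change from baseline for it, matching the treatment of MELD. A 0.3-point improvement is then -0.3 at every baseline, on the scale the ANCOVA already uses.

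In SAP 8.1, replace the two zero-baseline sentences with one rule: percent change is not calculated whenever the baseline is zero, whatever the later value. Absolute change then describes those participants.

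The cost is two wording edits and any matching change in the table shells, which are kept in a separate document. No new data are needed, and no interpretable information is lost.
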